## 8.3 Adverse Events

Adverse events will be coded using the Medical Dictionary for Regulatory Activities (MedDRA) Version 23.0 to identify the system organ class and preferred term.

Adverse events that occur or are reported to worsen in severity on or after date of first dose of study treatment in crossover phase period 1 will be considered to be TEAEs.

TEAEs will be categorized as occurring in a given study period according to the following rules:

- Adverse events that occur or are reported to worsen in severity on or after date and time of start of crossover period 1 study treatment and on or before date and time of end of crossover period 1 study treatment will be attributed to crossover study period 1. Adverse events that occur or are reported to worsen in severity on the start date of crossover period 1 study treatment that do not have a time associated with the event will be attributed to crossover study period 1.
- Adverse events that occur or are reported to worsen in severity after the end date of crossover period 1 study treatment and on or before the date of end of crossover period 2 study treatment will be attributed to crossover study period 2. Adverse events that occur or are reported to worsen in severity on the date of end of crossover period 2 study treatment that do not have a time associated with the event will be attributed to crossover study period 2.
- Adverse events that occur on the crossover date between crossover study period 1 and crossover study period 2 that do not have a time associated with the event will be attributed to crossover study period 1.
- Adverse events that occur in both crossover study period 1 and crossover study period 2 will be attributed to both crossover study periods.

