- Adverse events that occurred after the subject's last crossover study period will be classified as follow-up adverse events. If a subject entered both the first and second study periods, events occurring after the end date of the second study period will be considered as follow-up. If a subject discontinued prior to the start of the second crossover study period, any event occurring after the end date of the first crossover study period will be considered as follow-up. For subjects that did not enroll in the extension phase, any adverse event following the last crossover study period will be categorized as follow-up adverse events of the crossover phase. For subjects that did enroll in the extension phase, adverse events that occurred after the last crossover study period but before the start of the extension phase will be categorized as follow-up adverse events of the crossover phase.

The same period categorization rules will apply for the extension phase, where applicable, with the following exception. For the extension phase, if a subject only participates in the 4.4 grams/day dose stage of the extension phase, adverse events will only be categorized into the 4.4 grams/day treatment period or follow-up period within the extension phase. Otherwise, adverse events will be categorized into the 4.4 grams/day dose stage, the 6.7 grams/day dose stage, and follow-up as described above. For example, an adverse event that occurs in both the 4.4 grams/day dose period and the 6.7 grams/day dose period will be attributed to both extension phase treatment periods.

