TEAEs will be summarized for all subjects in the safety population. TEAEs will be summarized by treatment group for each dose in the crossover phase and for each dose in the extension phase. The total number of TEAEs occurring will be shown. The number and percentage of subjects experiencing any TEAE will also be provided. In addition, summary tables will reflect a count and percentage of subjects experiencing at least 1 TEAE in each system organ class and preferred term. All percentages will use the number of subjects in the safety population as the denominator. Therefore, if a subject has more than 1 AE within a system organ class, the subject will be counted only once in that system organ class. If a subject has more than 1 AE that codes to the same preferred term, the subject will be counted only once for that preferred term. Tabular summaries will be sorted by descending frequency by system organ class and by preferred term in the MS1819 treatment group.

Treatment-emergent AEs will be presented by treatment group and overall for the crossover phase and overall for the extension phase with percentages that use the number of subjects in the safety population as the denominator.

Treatment-emergent AEs will also be summarized by maximum relationship to study drug and maximum severity. Relationship to each study treatment (MS1819 and prestudy PERT [crossover phase only]) will be scored as Related or Unrelated. Severity will be rated as Mild, Moderate, or Severe. All percentages will use the number of safety subjects as the denominator. Summary tables will reflect a count and percentage of subjects experiencing at least 1 TEAE in each system organ class, preferred term and grouping, relationship, or severity. If a subject experiences more than 1 AE within a system organ class or preferred term, that subject will be counted only once for that event under the maximum severity or most related category for the study drug. Similarly, in the event that relationship or severity data are missing, the study analysis will follow the assumption of maximum relationship or severity in the summary tables. These summaries will be presented by treatment group and overall in the crossover phase and overall in the extension phase with percentages that use the number of subjects in the safety population as the denominator. The tabular summaries will be sorted by descending frequency by system organ class and by preferred term in the MS1819 treatment group.

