All AEs will be presented in data listings for subjects in the safety population.

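### Read literally, SAP 8.3 counts adverse events from the off-MS1819 gap between the two extension stages under 6.7 g/day, before the first 6.7 g/day dose

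*SAP*

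**What the plan says.** SAP 8.3 sorts treatment-emergent AEs in the crossover into period 1, period 2 and follow-up. Period 2 takes events that start or worsen "after the end date of crossover period 1 study treatment and on or before the date of end of crossover period 2 study treatment". Nothing requires that a period 2 dose has been taken. For a subject who entered both periods, "events occurring after the end date of the second study period will be considered as follow-up".

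The extension phase inherits this scheme: "The same period categorization rules will apply for the extension phase, where applicable, with the following exception". The exception is that, for subjects treated only in the 4.4 g/day stage, "adverse events will only be categorized into the 4.4 grams/day treatment period or follow-up period within the extension phase". All other subjects are sorted into the 4.4 g/day stage, the 6.7 g/day stage and follow-up by the rules already given. The accompanying example says that "an adverse event that occurs in both the 4.4 grams/day dose period and the 6.7 grams/day dose period will be attributed to both" stages.

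One off-treatment interval is handled expressly. For subjects who go on to the extension, "adverse events that occurred after the last crossover study period but before the start of the extension phase will be categorized as follow-up" events of the crossover phase. There is no matching sentence for the interval between the 4.4 and 6.7 g/day stages.

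On the design side, Protocol Table 3, footnote F, returns patients to their prestudy porcine PERT at the end of Visit 13. Protocol 11.3 opens the 6.7 g/day stage only if safety at 4.4 g/day is satisfactory and the CFA values fall short. It allows the same patients to take part in both stages.

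**The concern.** A period 2 that opens at the end of period 1 treatment suits a crossover without washout, because the end of one treatment is in practice the start of the next. The extension has no such adjoining boundary. A two-stage patient goes back to PERT, waits for the CFA results and safety review of the first 9 patients, and only then starts 6.7 g/day. Under the inherited rule that wait belongs to the 6.7 g/day stage.

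The extension's stated aim is to find a dose that is safe and brings CFA into a therapeutic range. A per-dose AE table that mixes events on 6.7 g/day with events that began on PERT describes that dose less cleanly than it should. With 9 to 14 patients in the stage, a single misplaced event is visible in the percentages.

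**Working it through.** The plan states no figure on this point, so there is none to reproduce. The check applies the rule to a timeline and compares the windows it creates.

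**1. Applying the rule.** Take period 1 as the 4.4 g/day stage and period 2 as the 6.7 g/day stage. The SAP does not write this mapping out, but its example of an event in both stages implies it. Suppose an AE begins three days after the last 4.4 g/day dose, while the patient is on PERT.
- It is treatment-emergent, because SAP 8.3 defines that from the first dose in crossover period 1. It therefore enters the tables.
- If the subject never enters 6.7 g/day, the exception applies and the event is follow-up.
- If the subject later enters 6.7 g/day, the exception does not apply. The event falls after the end of 4.4 g/day treatment and before the end of 6.7 g/day treatment, so it is filed under 6.7 g/day. Follow-up is not available, since it opens only after the second stage.

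**2. Windows within the 6.7 g/day column.**

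| Subject | 6.7 g/day event window opens |
|---|---|
| Enters 6.7 g/day directly from the crossover | At the start of that stage; earlier off-treatment events are crossover follow-up |
| Treated at 4.4 g/day, then 6.7 g/day | At the end of 4.4 g/day treatment, before any 6.7 g/day dose |

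Both kinds of subject are summarised together.

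**3. Scale.** SAP 8.3 sets the base: "All percentages will use the number of subjects in the safety population as the denominator". SAP 4.3 defines that population for each stage as those dosed in it. Protocol 11.3 plans 9 patients at 6.7 g/day, with 5 more possible, so 9 + 5 = 14. A subject whose only event attributed to 6.7 g/day began in the gap changes the incidence by:
- 1/9 = 11.1 percentage points with 9 patients
- 1/14 = 7.1 percentage points with 14 patients

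This is the weight of one subject, not an estimate of bias. The documents give neither the gap length nor an expected number of gap events.

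**4. With the window opened at the first 6.7 g/day dose**, no pre-dose day is counted under 6.7 g/day, whatever the gap length, and both rows of the table follow the same principle.

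**The case against.** The best defence is the qualifier in "The same period categorization rules will apply for the extension phase, where applicable, with the following exception". The inherited rule presupposes adjoining periods, and the SAP's treatment of the crossover-to-extension interval shows its general approach: off-treatment time after a treated segment is follow-up of that segment. A sensible programmer could apply the same principle here, and the table specifications, a separate document not available for this review, may already do so. This stands in part. The qualifier leaves latitude, but it names no other category for two-stage subjects, and the text that is written points to 6.7 g/day.

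Several stronger readings are tempting and are not supported:
- *That the rule contradicts many other parts of the SAP.* Days after 4.4 g/day being follow-up for one subject and second stage for another is how the crossover already treats subjects who stop after period 1. SAP 8.1's first-dose anchor governs only partial dates; if anything, it supports the sensible reading. SAP 8.6.3.1 concerns medications. The inconsistency with real force is with the crossover-to-extension gap, and hence the two windows in one column.
- *That the dose decision is compromised.* Protocol 11.3 has the DMC Chairperson evaluate safety after each initial group of 9, but no document says that evaluation uses the SAP 8.3 attribution. The DSMB review in SAP 10.1 takes place after the study is complete.
- *That a large bias is shown.* Any share of the 6.7 g/day window spent off drug depends on an assumed gap length and is a share of time, not of events.

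The error can also be found: "All AEs will be presented in data listings for subjects in the safety population", and SAP 8.2 lists first and last dose dates. Listings reveal the misplacement but do not correct the summary table.

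**Conclusion.** The rule is wrong as written, and the consequence is minor. Followed literally, SAP 8.3 places under 6.7 g/day any AE that starts or worsens after the end of 4.4 g/day treatment in a subject who enters both stages, including events that began on porcine PERT before the first 6.7 g/day dose.

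The conclusion assumes that the 6.7 g/day stage opens, that some patients enter both stages, that 4.4 and 6.7 g/day map to periods 1 and 2, and that the unseen table specifications do not override the text. The error inflates rather than conceals 6.7 g/day events, and it is confined to descriptive per-dose safety tables.

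**What to change.** Add to SAP 8.3, after the extension-phase exception:

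> For subjects treated in both extension stages, the 6.7 grams/day stage begins at the date and time of the first 6.7 grams/day dose. AEs with onset or worsening after the last 4.4 grams/day dose and before the first 6.7 grams/day dose are follow-up AEs of the 4.4 grams/day stage. Untimed AEs on the last 4.4 grams/day dose date are attributed to the 4.4 grams/day stage, and untimed AEs on the first 6.7 grams/day dose date to the 6.7 grams/day stage.

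The cost is three sentences and a small programming change, with no new data. The table specifications should be checked for agreement. The 4.4 g/day follow-up category grows slightly.

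Two neighbouring texts are best left alone. SAP 8.6.3.1 has no follow-up category for medications, and adding one for two-stage subjects only would treat them differently from 4.4 g/day-only subjects. Narrowing the example of an event in both stages to new onset or worsening in each could drop continuing events from 6.7 g/day. That would be a substantive change which this point does not call for.

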### 4.3 Safety Population

The safety population for the crossover phase, which will be used for all safety analyses of the crossover phase unless stated otherwise, will include all randomized subjects who receive at least 1 dose of treatment. Subjects in the safety population will be analyzed according to the actual treatment received regardless of their randomized assignment.

The safety population for each stage the extension phase, which will be used for all safety analyses of the extension phase unless stated otherwise, will include all subjects that enroll into the extension phase and receive at least 1 dose of treatment in the relevant stage of the extension phase.

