## 8. SAFETY EVALUATION

### 8.1 Overview of Safety Analysis Methods

Unless otherwise stated, safety analyses will be presented separately for each dose of the crossover phase and each dose of the extension phase. For the crossover phase, all safety analyses will be performed using the safety population and summarized by actual treatment (MS1819 regardless of period vs. PERT regardless of period) allowing direct intrasubject comparison of the tolerability of MS1819 vs. PERT. For the extension phase, all safety analyses will be performed using the safety population and summarized for each dose. Safety measures summarized will include AEs, laboratory data, vital signs, and concomitant medications. Additionally, exposure to study treatment during the study will be displayed.

Safety data will not be imputed, except for partial and missing dates, which will be imputed only for defining treatment-emergent AEs (TEAEs) and concomitant medications. Imputed dates will not be presented in data listings.

TEAEs will be defined as any AEs that occur or are reported to worsen in severity on or after the date of first dose of study treatment in crossover phase period 1. Partial dates will be imputed for the purposes of defining TEAEs as follows:

- For a missing start day where the month and year are present, the start day will be set to the first day of the month, unless 1) the first day of the month is before the date of first dose of study treatment and the month and year are the same as the month and year of the date of first dose of study treatment, and 2) the end date is on or after the date of first dose of study treatment or the end date is completely missing, in which case the start day will be set to the first day of first dose of study treatment.
- For a missing start day and month where the year is present, the start day and month will be set to January 1st, unless 1) January 1st is before the date of first dose of study treatment and the year is the same as the year of the date of first dose of study treatment, and 2) the end date is on or after the date of first dose of study treatment or the end date is completely missing, in which case the start day and month will be set to that of the date of first dose of study treatment.

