#### **8.4 Deaths, Serious Adverse Events, and Other Significant Adverse Events**

Treatment-emergent SAEs, TEAEs leading to study discontinuation, TEAEs resulting in death, treatment-emergent SAEs by relatedness, treatment-emergent SAEs leading to discontinuation, and treatment-emergent SAEs resulting in death will be summarized for all subjects in the safety population for each study phase. Summary tables will reflect a count and percentage of subjects experiencing at least 1 TEAE in each system organ class and preferred term within each AE subset (serious, leading to discontinuation, death). These summaries will be presented by treatment group and overall for each dose in the crossover phase and overall for each dose in the extension phase with percentages that

use the number of subjects in the safety population as the denominator. These tabular summaries will be sorted by descending frequency by system organ class and by preferred term in the MS1819 treatment group.

Adverse events leading to study discontinuation, AEs resulting in death, and SAEs will be presented in data listings for subjects in the safety population for each dose of the crossover phase and for each dose of the extension phase.

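### As worded, the SAP divides crossover adverse-event percentages by patients who may never have taken the column's treatment, so incidence in that column is understated if any patient leaves in period 1

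*SAP*

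**What the plan says.** The crossover safety population in SAP 4.3 "will include all randomized subjects who receive at least 1 dose of treatment"; either treatment qualifies. The same section adds: "Subjects in the safety population will be analyzed according to the actual treatment received regardless of their randomized assignment".

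SAP 8.1 presents crossover safety separately by dose, in two treatment columns (MS1819 and PERT), each pooled over periods.

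On denominators, SAP 8.3 states for the main tables "All percentages will use the number of subjects in the safety population as the denominator" and, for the relationship and severity tables, "All percentages will use the number of safety subjects as the denominator". SAP 8.4 has the percentages for serious events, deaths and discontinuations "use the number of subjects in the safety population as the denominator". SAP 8.6.3.1 sets the same denominator for concomitant medications. These rules cover the treatment columns and the overall column alike.

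SAP 8.3 also foresees early departure. Its follow-up rule has a clause beginning "If a subject discontinued prior to the start of the second crossover study period", under which later events of such a patient are classed as follow-up.

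The extension phase is treated differently: SAP 4.3 requires there that a patient "receive at least 1 dose of treatment in the relevant stage of the extension phase".

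**The concern.** In a crossover, exposure to each treatment is not guaranteed by membership of the safety population. A patient who stops in period 1 has taken one treatment only. Under the stated rule that patient counts in the denominator of both columns but can contribute on-treatment events to only one. Incidence in the other column is then too low.

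Safety is a primary objective (Protocol 6.1) and is assessed only descriptively (Protocol 10.6), so these percentages are the main safety result. SAP 8.1 offers the two columns for a direct within-patient comparison of tolerability. If unequal numbers leave early on the two treatments, the columns are diluted unequally and the comparison shifts as well as the levels.

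**Working it through.** **Inputs**
- About 30 completers, a 20% withdrawal allowance and about 36 enrolled (Protocol 7.3.1).
- 1:1:1:1 allocation over dose and sequence (SAP 2.4).
- OPTION: 41 enrolled; 5 withdrew during MS1819 and 3 during PERT; a ninth left after completing both periods (Protocol 5.6.3). The period of the 8 on-treatment withdrawals is not given.

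**The plan's own figure.** 30 × 1.2 = 36, which reproduces the planned enrolment. (Dividing instead, 30 / 0.8 = 37.5, gives 38; the difference does not matter here.) Then 36 / 2 = 18 per dose. I assume all 18 are dosed.

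**Formula.** Let N be the safety population in one dose arm and k the number who left in period 1 while on the other treatment. The column's exposed number is N − k, so

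reported incidence / correct incidence = (N − k) / N.

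**Range for one column, N = 18, 4 patients with an event.** The values of k are assumptions. For scale, 20% of 18 is 3.6, so k = 3 puts nearly all the planned loss in one treatment and one period.

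| k | Exposed | Reported (4/18) | Correct (4/exposed) | Reported is too low by |
|---|---|---|---|---|
| 0 | 18 | 22.2% | 22.2% | 0% |
| 1 | 17 | 22.2% | 23.5% | 5.6% |
| 2 | 16 | 22.2% | 25.0% | 11.1% |
| 3 | 15 | 22.2% | 26.7% | 16.7% |

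The last column is relative: 1 − (18 − k)/18.

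**OPTION pattern, by share of withdrawals in period 1.** The share is assumed, equal for both treatments, and all 41 are taken as dosed. The PERT column loses the early MS1819 withdrawals, and the MS1819 column loses the early PERT withdrawals.

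| Share in period 1 | PERT column factor | MS1819 column factor | True 40% in both, reported as (PERT / MS1819) |
|---|---|---|---|
| None | 41/41 = 1.000 | 41/41 = 1.000 | 40.0% / 40.0% |
| Half | 38.5/41 = 0.939 | 39.5/41 = 0.963 | 37.6% / 38.5% |
| All | 36/41 = 0.878 | 38/41 = 0.927 | 35.1% / 37.1% |

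With half in period 1, reported incidence is about 6% too low for PERT and 4% too low for MS1819. Scaled to 18 per dose, that is 5/41 × 18 / 2 = 1.1 patients missing from the PERT column and 3/41 × 18 / 2 = 0.7 from the MS1819 column.

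**The case against.** The strongest reply is that the as-treated sentences in SAP 4.3 and 8.1 already settle the matter: someone who never took PERT has no actual PERT treatment to be analysed under, so would not appear in that column. Context must be used in any case. The crossover safety population is defined once for both doses, yet the denominator is naturally read as the 18 in the displayed dose arm, and context might narrow it to the column's treatment too. The table specifications are a separate document, not available here, and may already use exposed numbers.

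Part of this stands. The intention may well be right, and then the fault is only in the wording. But the as-treated rule decides where a patient's data are counted and gives no denominator, whereas SAP 8.3, 8.4 and 8.6.3.1 do give one, repeatedly. The extension population carries an exposure condition that the crossover population lacks. Specifications using exposed numbers would depart from the SAP's literal text, and the two should agree.

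It is also fair that the effect can be seen and undone. Counts are shown beside percentages (SAP 3), disposition by period and sequence is tabulated (SAP 5.1), exposure is summarised by treatment and period (SAP 8.2), and all events are listed (SAP 8.3). No test or decision rule is stated for these percentages. That limits the harm but does not make the printed percentages right.

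A reader might infer from OPTION's 5 against 3 that the rule would hide harms of MS1819. The documents do not support that. Only period-1 withdrawals matter, their number is not given, and with similar timing on both treatments it is PERT incidence that is understated more.

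**Conclusion.** The point holds, conditionally. Followed literally, the stated denominator understates incidence in the column of any treatment that some safety-population patients never took. If nobody leaves in period 1 there is no error, and withdrawals in period 2 do not contribute.

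Under the assumed range of 0 to 3 unexposed patients among 18 per dose, the reported percentage is 0% to 17% too low in relative terms. The upper end is unlikely. The OPTION pattern with half the withdrawals early suggests about 6% for PERT and 4% for MS1819.

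The text does not support saying that the tables will certainly be wrong, since the table specifications may already be correct. CFA and the other efficacy summaries are unaffected. This should be corrected, but it does not threaten the trial.

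**What to change.** In SAP 8.3, 8.4 and the concomitant-medication part of 8.6.3.1, state that each crossover treatment column takes as its denominator the safety-population subjects in that dose arm who took at least one dose of that treatment, and that the overall column takes all safety-population subjects in that dose arm. State also that the table specifications must match, and check that they do.

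The cost is one sentence, applied in three sections. It needs no new data and changes no study procedure. If the programmers already work this way, no output changes.
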